8.4 STUDY ENROLLMENT PROCEDURES

8.4.1 Recruitment and screening

All subjects with lumbar spinal stenosis will be considered for screening into the study. Subjects expressing an interest in participation will proceed with the consent process as per Section10.1..

8.4.2 Patient Informed Consent

Potential patients will be asked to sign a consent form after verbal explanation of the study by the consenting PI or appropriate designee.

CONFIDENTIAL

The PI explains to each subject the nature of the investigation, its purpose, the procedures involved, the expected duration, the potential risks and benefits and any discomfort it may entail. Each subject is informed that the participation in the investigation is voluntary and that he/she may withdraw from the investigation at any time and that withdrawal of consent will not affect his/her subsequent medical assistance and treatment. The subjects are informed that he/she can ask any question, and consult with family members, friends, their treating physicians or other experts before deciding about their participation in the investigation. Enough time is given to the subjects.

The subjects are informed that authorised individuals other than their treating physician may examine his/her medical records. All subjects a given a subject information sheet and a consent form describing the investigation and providing sufficient information for the subjects to make an informed decision about their participation in the investigation. The formal consent of a subject, using the approved consent form, is obtained before the subject is submitted to any investigation procedure. The subject should read, understand, and voluntarily agree before signing and dating the informed consent form, and is given a copy of the signed document. The consent form is signed and dated by the subject and the PI (or her/his designee). The signed consent form it is retained as part of the investigation records.

If new information becomes available that can significantly affect a subject's future health and medical care that information shall be provided to the subjects affected in written form. If relevant, all affected subjects shall be asked to confirm their continuing informed consent in writing.

Consent will not denote enrolment into the study. Subjects are enrolled at the time of incision.

8.4.3 Subject Identification

Subjects who consent to participate shall be assigned a unique Subject Identification Number to deidentify their information. This Subject Identification Number will be captured on the Screening & Enrollment Log and used to identify them on all source documents and eCRFs thereafter.

A record of all screened subjects will be maintained in a Screening/Enrollment Log. The date of screening, results of screening (included or not) and, if not eligible, the primary reason for excluding the subject, enrollment status (enrolled or not) and, if not enrolled, the primary reason will be recorded.

Please note, for purposes of the study population a subject is considered enrolled at the time of surgical incision.

8.6 SUBJECT TREATMENT ASSIGNMENT

Following screening, all subjects will be assigned to treatment with the Lobster device.

9. TECHNICAL AND TREATMENT FAILURES

Technical failures are subjects that are considered eligible for the study per the inclusion and exclusion criteria, enrolled at the time of incision, but did not complete the study treatment/ procedure due to safety concerns from the implanting surgeon (i.e., anatomical difficulties, issues noted during procedure, etc.).

These subjects will be included in the enrollment totals but will be withdrawn from the study and follow-up will be discontinued at the time of technical or treatment failure.

Treatment failures are subjects that must undergo a different procedure other than the study treatment (i.e. use of a different interspinous spacer or conversion to fusion) due to an intraoperative injury or damage to the investigational/ control device during an attempted implantation leading to safety concerns and a subsequent change in treatment. These subjects will be included in the enrollment totals but will be withdrawn from the study and follow-up will be discontinued at the time of technical or treatment failure.

Patients that have not passed screening will not be enrolled in the study and further follow-up of these patients shall proceed according to the hospital standard procedures.

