12.4 USE OF DATA FROM EARLY DISCONTINUATION CASES

Study data collected previously for subjects who withdraw from the study, are discontinued from the study by the Investigator or LTFU will be included in the data analysis and clinical study report.

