16. SAFETY REPORTING

16.1 DEFINITION AND ASSESSMENT OF (SERIOUS) ADVERSE EVENTS AND OTHER SAFETY RELATED EVENTS

AEs/DDs will be reported according to MDR Regulation (EU) 2017/745 and ISO 14155:2020, while recognizing and following other specific laws, regulations, directives, standards and/or guidelines, as appropriate, as required by the country(ies) in which the study is conducted.

The list of foreseeable AEs and anticipated adverse device effects, together with their likely incidence, mitigation or treatment are detailed in the Investigator Brochure (IB) and IFU of the medical device used in this study.

As detailed in the CIP, events of the following types are captured for all subjects throughout the study, between the start time of enrolment and the end of subject participation (i.e., completion of the study or withdrawal of consent).

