16.3 REPORTING PROCEDURES AND TIMELINES

16.3.1 Documentation

Device deficiencies (DD) and all adverse events (AE) including all serious adverse events (SAE) are collected, fully investigated and documented in the source document and appropriate case report form (CRF) during the entire investigation period, i.e. from the operating room when the initial incision(s)

CONFIDENTIAL

is made to start the implantation procedure until the last CIP specific procedure, including a safety follow-up period.

- Documentation of AEs (including SAEs) by the PI includes diagnosis or symptoms, start and stop dates of event, event treatment, event resolution, assessment of severity, seriousness and causal relationship to device and/or investigation procedure.
- Documentation of DDs by the PI includes description of event, start date, investigational device information, action taken with regard to the investigational device, and whether the DD led to an AE. The Sponsor shall review all DDs and determine and document in writing.

The investigator will follow each subject who experiences an AE until the event resolves, resolves with sequelae, or no further improvement is expected. In the unusual circumstance that an AE has not resolved by the time of the subject's completion of the study, an explanation will be entered

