19. STATISTICAL METHODS

19.1 ANALYSIS SETS

The analysis data sets will be defined in a way that mirrors the Superion P140004 study.

The primary analysis cohort for this study will be the Modified Intent-to-Treat Cohort, defined as: Modified Intent-to-treat patient population (mITT): The mITT patient population will include all patients having an anesthesia start time. Subjects with an anesthesia start time but that do not receive the device will be failures.

Confirmatory analysis will be performed in the Per Protocol Cohort, defined as: Per protocol (PP) Population: The PP patient population will include all subjects with 12-month follow-up data and no major protocol deviations and subjects that failed before 12 months

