19.4 SAFETY ANALYSES

Assessment of the safety of the investigational implant will include an evaluation of the incidence and severity of complications and adverse reactions associated with the treatment. Adverse event rates will be summarized by type of AE and for specific AEs in two ways: 1) per patient incidence of specific AEs and classes of AEs and 2) by event, summarizing event counts by visit interval over time and in accordance with FDA Guidance. Device and procedure-related events will be summarized by severity and relatedness. Events listings that include details such as relatedness, severity, onset and resolution status will be provided for all events and relevant subsets of events such as serious events and related events. Primary safety comparisons will be performed using the mITT analysis set. The summary tables will show the adverse events (in coded terms), the total number of events, and the number and the percentage of subjects affected in each treatment group ("subject wise evaluation") and stratified by relation to device and severity.

CONFIDENTIAL Page 60 of 67 The event rates observed in the Superion SSED (P140004) will be used as clinical guideposts only. There is no formal statistical hypothesis test on these endpoints. Please note that the primary endpoint captures both safety and effectiveness, and therefore these events are considered interesting but appropriately evaluated in this framework. Additional details regarding the safety comparisons will be provided in the SAP.

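### Section 9 ends follow-up of technical and treatment failures at the failed procedure, but section 16.1 keeps safety capture open for all subjects until study completion or withdrawal of consent

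*Protocol*

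**What the plan says.** Protocol section 9 defines two groups. Technical failures are eligible subjects, enrolled at incision, whose procedure is not completed because of the surgeon's safety concerns. Treatment failures are subjects who need a different procedure after an intraoperative injury or damage to the device. For each group it says that they count in the enrollment totals but "will be withdrawn from the study and follow-up will be discontinued at the time of technical or treatment failure".

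Section 16.1 has a wider window: "events of the following types are captured for all subjects throughout the study", from enrolment to "the end of subject participation (i.e., completion of the study or withdrawal of consent". Section 16.3.1 has adverse events documented from the first incision "until the last CIP specific procedure, including a safety follow-up period". It gives no length for that period. It also says: "The investigator will follow each subject who experiences an AE until the event resolves" or reaches a stable outcome.

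In the analysis sections, 19.1 puts everyone with an anesthesia start time in the mITT set and adds: "Subjects with an anesthesia start time but that do not receive the device will be failures". Section 19.4 says: "Primary safety comparisons will be performed using the mITT analysis set". Section 12.4 covers the data of discontinued subjects: "Study data collected previously for subjects who withdraw from the study" are to be analysed. It says nothing about data arising afterwards.

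**The concern.** The protocol gives sites two instructions for the same subjects and does not say which prevails. Under section 9, data collection stops on the day of the failed procedure. Under section 16.1 it continues, because withdrawal by protocol rule is neither completion nor withdrawal of consent. The three sites could act differently.

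These subjects are in the denominator of the primary safety result, which section 7.4 defines as the incidence of major device- or procedure-related complications. Deep infection, neurological deficit, spinous process fracture and death can all first appear after day 0, even in a subject who left without the implant. The group is also not a random subset, because an intraoperative problem defines it. The SAP can decide how to score such subjects, but it cannot supply events that sites were told not to collect. What is at stake is the completeness of a descriptive safety rate.

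**Working it through.** **1. The passages side by side**

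| Question | Section 9 | Section 16.1 | Section 16.3.1 |
|---|---|---|---|
| Who | Technical and treatment failures | All subjects | All AEs and device deficiencies |
| Start | Enrolled at incision | Enrolment | Initial incision |
| End | The failed procedure | Study completion or withdrawal of consent | Last protocol-specific procedure, plus a safety follow-up period |

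Sections 8.4.3 and 9 both place enrolment at incision, so these people are study subjects when the failure occurs and section 16.1 covers them. The conflict between 9 and 16.1 is direct. The conflict with 16.3.1 is softer: for such a subject the last protocol-specific procedure could be the failed implantation itself. Even then, the added safety follow-up period does not fit with stopping at the failure.

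**2. What is and is not lost if section 9 is followed**

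- An event at the failed procedure is recorded and followed to its outcome (16.3.1). Section 16.4 also has the investigator treat device-related events until they resolve or no further improvement is expected.
- Vigilance reporting continues (16.3.5), so a later serious device incident may reach the sponsor, though not necessarily the trial database.
- A new first complication after day 0 is not clearly covered by any trial collection rule.

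**3. Effectiveness and sample size**

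Section 19.3 uses p0 = 0.611, p1 = 0.711, one-sided alpha 0.05 and power 85%:

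n = [(1.645 × √(0.611 × 0.389) + 1.036 × √(0.711 × 0.289)) / 0.100]² = 161.7, so 162.

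162 / (1 − 0.15) = 190.6, so 191.

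Both stated figures reproduce. Section 19.1 counts subjects without the device as failures in the composite, so ending their follow-up changes neither the effectiveness result nor this calculation.

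**4. How many subjects**

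The only frequency in the protocol is in section 3.3: one procedure not completed in the retrospective study that aims to follow 225 subjects. Taking 225 as the denominator is an assumption.

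- Share: 1/225 = 0.44%, exact (Clopper-Pearson) 95% CI 0.01% to 2.45%.
- Expected among 191: 191/225 = 0.85 (CI 0.02 to 4.7). Among 250: 250/225 = 1.1.
- Chance of at least one among 191: 1 − (1 − 1/225)^191 = 0.57.

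**5. Size of the effect on the safety rate**

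If one subject's first complication were missed and that subject were scored event-free, the rate would fall by 1/191 = 0.52 percentage points, or 1/250 = 0.40 points. For scale only, a 95% interval around an 11.3% rate in 191 subjects has half-width 1.96 × √(0.113 × 0.887 / 191) = 4.5 points. The 11.3% is the device-only complication figure in section 3.3. It includes bone remodelling and serves here only as an illustrative overall rate.

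The expected shift cannot be computed. The protocol gives no late-complication risk for subjects who leave without the implant, and its rates for implanted patients are not a fair substitute. The one documented uncompleted procedure was stopped for a spinous process fracture, which section 7.4 lists as a safety event. That subject would already count on day 0, so a per-patient incidence would lose nothing.

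**The case against.** The strongest reply is that 16.1 is loose shorthand and section 9 is the specific rule. Section 12.1 also lets investigators withdraw subjects who have not withdrawn consent, so the 16.1 definition omits every such withdrawal. That is plausible, but it only means that 16.1 may be the text to correct. The passages still differ and still need reconciling.

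A second reply is that scoring and missing-data handling are left to the SAP (19.4, 19.6). This stands against any firm claim of bias. It does not answer the collection question, which the protocol settles.

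A third reply is that the effect is negligible: about one subject is expected, some of these subjects will already count on day 0, and section 19.4 has no formal safety test. This stands and limits the weight of the point.

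A reader might infer three stronger things that the documents do not support:

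- **That the complication rate will be biased downward.** This needs a late first event in a subject with no day-0 event, and event-free scoring of that subject. The protocol establishes neither.
- **That all later harm in these subjects goes unseen.** Follow-up of existing events, treatment of device-related events and vigilance reporting all continue.
- **That the effectiveness result benefits.** Section 19.1 already scores these subjects as failures.

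**Conclusion.** The point holds as a minor inconsistency with a narrow consequence. Section 9 contradicts section 16.1, and more softly 16.3.1, on when safety collection ends for technical and treatment failures, who remain in the primary safety set. If section 9 is followed, new related complications after day 0 need not be collected in the trial.

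About one such subject is expected in 191, and up to about five at the upper confidence limit. This rests on one case and the assumed denominator of 225. The effect on the reported rate is very small and cannot be quantified reliably from the protocol. Its direction would be downward only under event-free scoring. If these subjects are treated as missing or censored, there is no such mechanical shift, but their later events remain unknown.

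**What to change.** Reconcile sections 9, 16.1 and 16.3.1 so that one safety-data collection window applies to every subject in the mITT safety set. One way is to limit the discontinuation in section 9 to effectiveness assessments and let safety-event collection for these subjects follow the 16.1 and 16.3.1 window. State the length of the safety follow-up period in 16.3.1. Refer to that common window rather than to a named visit: 7.1 and 10.4 schedule follow-up to 24 months, so a separate 12-month limit would create a new mismatch.

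Report these subjects' events within the mITT complication rate and also separately, because a later event may belong to the alternative procedure.

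The cost is a wording change and safety contacts for a few subjects, roughly one to five on the figures above. The reported complication rate may become slightly less favourable. Attribution will stay uncertain for subjects who received another procedure.

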10. STUDY PROCEDURES

10.1 INFORMED CONSENT (ICF)

Potential patients will be asked to sign a consent form after verbal explanation of the study by the consenting PI or appropriate designee.

The PI explains to each subject the nature of the investigation, its purpose, the procedures involved, the expected duration, the potential risks and benefits and any discomfort it may entail. Each subject is informed that the participation in the investigation is voluntary and that he/she may withdraw from the investigation at any time and that withdrawal of consent will not affect his/her subsequent medical assistance and treatment. The subjects are informed that he/she can ask any question, and consult with family members, friends, their treating physicians or other experts before deciding about their participation in the investigation. Enough time is given to the subjects.

The subjects are informed that authorised individuals other than their treating physician may examine his/her medical records. All subjects a given a subject information sheet and a consent form describing the investigation and providing sufficient information for the subjects to make an informed decision about their participation in the investigation. The formal consent of a subject, using the approved consent form, is obtained before the subject is submitted to any investigation procedure. The subject should read, understand, and voluntarily agree before signing and dating the informed consent form, and is given a copy of the signed document. The consent form is signed and dated by the subject and the PI (or her/his designee). The signed consent form it is retained as part of the investigation records.

If new information becomes available that can significantly affect a subject's future health and medical care that information shall be provided to the subjects affected in written form. If relevant, all affected subjects shall be asked to confirm their continuing informed consent in writing.

Consent will not denote enrolment into the study. Subjects are enrolled at the time of incision.

10.2 SCREENING VISIT [WITHIN 60 DAYS Of SURGERY]

Upon successful documentation of informed consent, a preoperative screening visit will be performed within 60 days prior to the patient's surgery and will serve as a Standard of Care (SOC) evaluation by the Investigator to confirm patient eligibility.

NOTE: The subject recruitment and screening process should follow the study enrollment procedures outlined in Section 8.4. All Patient Reported Outcome Questionnaires (PRO) should be administered prior to any other study visit assessments or procedures being performed to prevent information from the examination biasing the subject's responses.

- Informed consent
- Inclusion/exclusion criteria review
- Demographics collection
- Medical history collection
- Physical examination
- Neurological examination
- Patient Reported Outcome (PRO) Questionnaires
 - VAS (back and leg)
 - o ODI
 - SF-12
 - o ZCQ
- Radiographic Imaging
 - o X-rays
 - CT scans (or MRI if available in lieu of CT)

10.5 LATE AND MISSED VISITS

If a subject fails to return for a scheduled study visit within the visit window defined in the study protocol but completes the visit prior to the beginning of the next visit window, that visit is considered to have been completed late. A protocol deviation should be documented on the appropriate eCRF.

If a subject fails to return for a scheduled study visit within the visit window defined in the study protocol and the next scheduled study visit window opens, that visit is considered to have been missed. A protocol deviation should be documented on the appropriate eCRF.

All attempts should be made to schedule the subject for the study visit as soon as possible so that it is captured late rather than missed completely.

10.6 UNSCHEDULED VISITS

Subjects may be seen for unscheduled postoperative visits as needed. Data from unscheduled visits that relate to the index operation will be collected and reported as an Unscheduled Visit for this study. Unscheduled visits that do not relate to the index operation should be evaluated on a case-by-case basis by the Investigator to determine if they need to be reported as an Unscheduled Visit for this study.

For Unscheduled Visits relating to the index operation, the Investigator will assess the subject's progress and perform the following:

- PROs
 - VAS (back and leg)
 - ODI
 - SF-12
 - Patient satisfaction survey
 - ZCQ
- Neurological examination
- Record any new or updated adverse events and device deficiencies, if applicable
- Radiographic Imaging
 - X-rays
 - CT scans
- Review postoperative rehabilitation regimen with the subject

CONFIDENTIAL Page **42** of **67**

[Diametros Medical, LB2CT]

[Project version: 1.0, 08-09-22]

10.7 STUDY COMPLETION/DISCONTINUATION

The completion of this clinical investigation will be with the final follow-up visit (at 12 months) of the last enrolled patient. At the end of the study, further follow-up of these patients shall proceed according to the hospital standard procedures.

10.8 DATA COLLECTION SUMMARY

Table 10-1 below outlines the schedule of visits to be attended by the subject during his/ her participation in the study. The schedule spans the subject's enrollment to their last prescribed follow-up. Defined in the table are the tasks to be performed by the investigator and subject at each visit, including the examination(s) and imaging procedures as well as the types of information to be collected. Provided in parentheses next to each visit are the upper and lower acceptable bounds for the timing of the visit.

Table 10-1. Clinical Visits – Scheduling and Requirements

Activity	Screening (within 60) days prior to surgery)	Ir	ndex Proced (Day 0)	ure	6-week (+/- 14 days)	3-M (+/- 14	o days)	6- Mo (+/- 28 days)	12- Mo (+/- 60 days)	Annual thereafter until final subject reaches 12-Mo (+/- 60 days)	Unscheduled
Informed Consent	Х		-		-	-		-	-	-	-
Inclusion/Exclusion Criteria (including DXA, if needed)	Х		Х		-			-	-	-	-
Demographics	Х	-					-	-	-	-	
Medical History	Х	-			-	-		-	-	-	-
Pregnancy Test	-	X			-	-		-	-	-	-
Radiographs (standing, lateral, neutral) and CT	Х	X			Х	X		Х	Х	Х	Х
ODI	Х		-		Х	X		Х	Х	Х	Х
ZCQ	Х	Х	Х	-	Х	X		Х	Х	Х	Х
VAS	Х		-		Х	X		Х	Х	Х	Х
Patient Satisfaction	-		-		Х	X		Х	Х	Х	Х
SF-12	Х		_		Х	X		Х	Х	Х	Х
Physical Exam	Х	-			Х	X		Х	Х	Х	Х
Neurological Exam	Х	-			Х	X		Х	Х	Х	Х
Record/Review Concomitant Medications	Х	Х			х	X		X	Х	Х	Х
Record/Review Adverse Events and Device Deficiencies	-		X		Х	X		X	X	X	Х

CONFIDENTIAL

